**F. FOLLOW-UP**

Follow up will begin on the index date, and end on the first occurrence of anaphylaxis or one day after the index date, whichever occurs first.

**G. ANALYSIS**

**1. Sites with zero outcome events or use of only one iron product**

Because anaphylaxis is a rare outcome, and because we had several sites in the feasibility analysis with zero anaphylaxis events, we expect there will be several sites in the actual assessment with zero anaphylaxis events. We will exclude Data Partner sites that have no outcome events, after medical record review, from the inferential analysis described in section G5. Because our final outcome is a risk ratio rather than a risk difference and because all analyses will stratify on site, Data Partner sites with zero outcome events will contribute no data to the relative risk analysis. We believe the bias introduced by combing sites with different prescribing and coding practices and treating them as a single site to be potentially significant. Similarly, sites which use only one parenteral iron product will be excluded from the inferential analysis. However, when calculating the absolute incidence, we will perform our analysis without and without sites with zero outcome events or use of only one iron product (See section G3 below).

**2. Comparison of baseline characteristics**

We will compare the baseline characteristics between new users of iron dextran and new users of other iron products, overall and at each Data Partner (Table 5). We will use standardized differences, which is less sensitive to sample size than p-values in t-tests or Chi-square tests, for the comparisons. A value of 0.1 or greater indicates meaningful covariate imbalance.

**Table 5. Baseline characteristics**

	Iron dextran N (%)	Other parenteral iron products N (%)
Age on index date 0-4 years 5-18 years 19-44 years 45-64 years 65 and older		
Gender Female Male		
History of anaphylaxis, not related to food		
Drug allergy		
Atopic dermatitis		
Food, latex, insect bite allergy		
Other allergy		
Allergic rhinitis		
Asthma		
HIV infection		
COPD		

	Iron dextran N (%)	Other parenteral iron products N (%)
Coronary heart disease		
Hypertension		
Immunosuppressive therapy		
Oral steroid use		
Injectable steroid use		
Antibiotic use		
Beta blocker use		
ACE inhibitor use		
ARB use		
Year of new use		
2000		
2001		
2002		
2003		
2004		
2005		
2006		
2007		
2008		
2009		
2010		
2011		
2012		

	Iron dextran N (%)	Other parenteral iron products N (%)
2013		
Clinical setting where IV iron is administered* Outpatient Inpatient Emergency department		

\* Use on the index date; for patients receiving IV iron in more than one clinical setting on the index date, report use in each setting for which it is documented

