**E. IDENTIFICATION OF COVARIATES**

Table 4 lists the covariates the workgroup will obtain from the 183-day period preceding (and including) the index date. Age on index date and gender will be identified from the MSDD’s demographic files. Diagnostic codes recorded during inpatient, outpatient, or emergency department encounters will be obtained from the MSDD’s diagnosis file.

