**Table 4. ICD-9-CM codes to identify covariates**

Confounder	Categorization	Identified by ICD-9-CM code(s) (unless otherwise noted)
History of anaphylaxis, not related to food*	Yes/No	995.0, 999.4, V13.81
Drug allergy*	Yes/No	995.27, V15.08, V14
Atopic dermatitis	Yes/No	691.8
Food/insect/latex allergy*	Yes/No	V15.01, V15.02, V15.03, V15.04, V15.05, V15.06, 995.6, V15.07
Other allergy*	Yes/No	995.3, 518.6, 558.3, 708, V15.09
Allergic rhinitis	Yes/No	477
Asthma	Yes/No	493
HIV infection	Yes/No	V08, 042
Chronic obstructive pulmonary disease (COPD)	Yes/No	491, 492, 496
Coronary heart disease	Yes/No	413, 414
Primary hypertension	Yes/No	401
Immunosuppressive therapy	Yes/No	Outpatient pharmacy dispensing file using National Drug Codes and procedure file for identifying HCPCs codes for selected immunosuppressives (alefacept, azathioprine, basiliximab, belatacept, non-ophthalmic cyclosporine, glatiramer, mycophenolate, sirolimus, and non-topical tacrolimus), selected

Confounder	Categorization	Identified by ICD-9-CM code(s) (unless otherwise noted)
		immunomodulators (abatacept, adalumumab, anakinra, canakinumab, certolizumab, dimethyl fumarate, etanercept, fingolimod, golimumab, infliximab, lenalidomide, mitoxantrone, natalizumab, pomalidomide, rilonacept, teriflunomide, thalidomide, tocilizumab, and ustekinumab), a selected antirheumatic kinase inhibitor (tofacitinib), selected monoclonal antibodies (alemtuzumab, ofatumumab, and rituximab), or an alkylating agent (cyclophosphamide)
Oral steroid use* †	Yes/No	Outpatient pharmacy dispensing file using National Drug Codes
Injectable steroid use* †	Yes/No	Outpatient pharmacy dispensing file using National Drug Codes and procedure file for identifying HCPCs codes
Antibiotic use †	Yes/No	Outpatient pharmacy dispensing file using National Drug Codes
Beta blocker use †	Yes/No	Outpatient pharmacy dispensing file using National Drug Codes
ACE inhibitor use †	Yes/No	Outpatient pharmacy dispensing file using National Drug Codes
ARB use †	Yes/No	Outpatient pharmacy dispensing file using National Drug Codes
Year of new use	Number	n/a
Clinical setting where IV iron administered	Inpatient, outpatient, emergency	n/a

Confounder	Categorization	Identified by ICD-9-CM code(s) (unless otherwise noted)
	department	

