## 5. Analysis comparing risk of anaphylaxis between parenteral iron dextran and other iron products

### a. Estimation of relative risk

We will employ two propensity score-based approaches – matching and stratification – to investigate the association between the use of iron dextran and anaphylaxis, with use of other parenteral iron products as the comparison group. We will assess the covariate balance after matching and stratification. The propensity score is defined as the probability of receiving iron dextran given the measured confounders. We use the propensity score methods as our primary approach because the number of anaphylaxis events is expected to be small and the number of confounders is relatively large. The propensity score approach overcomes this issue by allowing us to adjust for all measured confounders simultaneously through a composite summary score. We will estimate the propensity scores by site using a logistic model common to all Data Partners using the probability of receiving iron dextran as the dependent variable and covariates in Table 5 as independent variables.

Propensity score matching will be conducted within sites. We will match one iron dextran user with one other iron product user using 1:1 nearest-neighbor matching without replacement

with a caliper of 0.05. Unmatched patients will be excluded from subsequent analyses. Each Data Partner will transfer an aggregated dataset of the matched cohort, which includes only the number of users and outcome events in each treatment group, to the project team. The project team will then estimate the odds ratio of the confirmed anaphylactoid/anaphylaxis event, from the Sampson criteria, comparing iron dextran users with other iron product users. The aggregated dataset will only include the number of users and outcome events within each treatment group. By matching one iron dextran user with one other iron product user with similar propensity score, we estimate the average treatment effect among the treated (ATT). Thus, we will also do propensity score stratification to estimate the population-wide average treatment effect (ATE).

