In propensity score stratification, each Data Partner will divide its entire study population (iron dextran users and other iron products users) into 5 strata based on the site-specific propensity score quintiles. Each Data Partner will transfer an aggregated dataset consisting of the within-stratum numbers users and anaphylaxis events in each treatment group. If sample size allows, the project team will fit a logistic regression model on the probability of anaphylaxis comparing the exposure groups (iron dextran vs. other iron products) stratifying both on site and within-site propensity score strata. If the number of anaphylaxis events is too small to stratify on both site and the within-site PS strata, we will consider stratifying on PS strata only or collapsing certain sites with few anaphylaxis events. The results from the propensity score matching and stratification analyses could differ if the effect of iron dextran differs among the subgroup of actual iron dextran users (ATT) versus among the entire group of all parenteral iron products users (ATE).

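### The propensity model is pointed to Table 5, which shows age only in five bands; if age is entered that way, some age confounding can remain in both primary estimates

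*Protocol*

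**What the plan says.** Protocol II.G.5.a specifies a logistic propensity model, common to all Data Partners and fitted at each site, with "covariates in Table 5 as independent variables". In Table 5 the age entry reads "Age on index date 0-4 years 5-18 years 19-44 years 45-64 years 65 and older".

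Three other places bear on this:

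- II.E says "Age on index date and gender will be identified from the MSDD’s demographic files". A patient-level age is therefore held at each site; the bands could not be formed without it.
- Table 4, which gives a categorisation for the other covariates, has no row for age.
- II.G.2 introduces Table 5 as a descriptive comparison: "We will compare the baseline characteristics between new users of iron dextran and new users of other iron products, overall and at each Data Partner". It uses standardised differences, with 0.1 or more read as meaningful imbalance.

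Both primary analyses rest on this score. For matching, "We will match one iron dextran user with one other iron product user using 1:1 nearest-neighbor matching without replacement" (caliper 0.05, within site). For stratification, each site's users are divided "into 5 strata based on the site-specific propensity score quintiles". The secondary outcome regression in II.G.6.a adjusts for the same confounders.

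**The concern.** A programmer who follows II.G.5.a to Table 5 finds one form of age: five bands. Children are probably few, so the score would in effect see three adult bands, two of them 20 years or more wide and the last open-ended. Patients at opposite ends of a band who agree on every other covariate would get the same score.

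Four features of the design make the form of age worth settling:

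- II.H.2 names prescribing for different reasons as the route of confounding, but the Table 6 indications are not in Table 5 and so not in the score. Age and sex are among the few modelled variables that may stand in for indication.
- Matching, stratification and the secondary regression would share the same coding of age, so agreement between them would not reveal a problem.
- Standardised differences on the bands cannot show imbalance within a band.
- Sites send only counts of users and events. The project team could not re-adjust for age later without rerunning the site programs.

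**Working it through.** **1. The plan's own figures.** No stated figure depends on the form of age. Table 7 is only the yardstick. Two-sided Fisher exact power (doubled one-tail p-value, 40,015 v 60,714 users) gives 80.7% against the stated 81.3% at 2.05 per 10,000 and relative risk (RR) 2.80, and 80.9% against 81.1% at 9.50 per 10,000 and RR 1.70. All 12 rows agree within 0.6 points.

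**2. Inputs.** From the protocol: the five bands, and a dextran share of 40,015/(40,015 + 60,714) = 39.7%. Assumed, because the protocol gives none of them:

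- age normal with mean m and SD s, restricted to 0-100;
- odds of receiving dextran multiplied by θ per decade of age;
- anaphylaxis risk multiplied by γ per decade, equally in both arms, so the true RR is 1.

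**3. Formulas.**

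- P(dextran | age) = expit[a + ln θ × (age − m)/10], with a chosen to give 39.7% overall.
- Crude RR = mean of γ^(age/10) among dextran users, divided by the same mean among other users.
- Banded RR = Σ w_b R1_b / Σ w_b R0_b, where w_b is the share of all users in band b and R1_b, R0_b are the arm-specific mean risks there.
- Share of confounding left = ln(banded RR) / ln(crude RR).
- With age as the only covariate, a continuous-age score is monotone in age, so its quintiles are age quintiles and the same formula applies.

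**4. Results (true RR 1).**

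| m (s) | θ, γ | Crude RR | Five bands (share left) | Quintiles of continuous-age score (share left) |
|---|---|---|---|---|
| 45 (16) | 1.16, 1.2 | 1.069 | 1.010 (15%) | 1.007 (11%) |
| 45 (16) | 1.35, 1.5 | 1.337 | 1.048 (16%) | 1.040 (14%) |
| 55 (17) | 1.16, 1.2 | 1.076 | 1.013 (17%) | 1.007 (10%) |
| 55 (17) | 1.35, 1.5 | 1.362 | 1.064 (20%) | 1.038 (12%) |
| 65 (15) | 1.16, 1.2 | 1.057 | 1.015 (27%) | 1.005 (9%) |
| 65 (15) | 1.35, 1.5 | 1.262 | 1.076 (32%) | 1.024 (10%) |

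Example, last row: ln 1.076 / ln 1.262 = 0.0733/0.2327 = 0.32. The share left by the bands grows with mean age because the top band is open-ended.

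If dextran use falls with age while risk rises, the residual goes the other way. With θ = 1/1.35, γ = 1.3 and m = 45, the banded RR is 0.971 and the quintile RR 0.979. With θ = 1/1.35, γ = 1.5 and m = 65, they are 0.931 and 0.977.

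**5. Matching.** I simulated 12 equal sites (about 100,729 users in total) with dextran share rising from 5% to 85%, site-level scores, and 1:1 nearest-neighbour matching without replacement at caliper 0.05 on the probability scale. Age was the only covariate. Expected risks were compared, so there is no event noise.

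| m (s) | θ, γ | Matched RR, bands | Matched RR, linear plus quadratic age |
|---|---|---|---|
| 55 (17) | 1.16, 1.2 | 1.020 | 1.012 |
| 55 (17) | 1.35, 1.5 | 1.077 | 1.017 |
| 65 (15) | 1.35, 1.5 | 1.091 | 1.017 |
| 65 (15) | 1/1.35, 1.5 | 0.925 | 0.984 |

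At m = 65, θ = 1.35 and γ = 1.5, the mean age gap left between matched arms is 1.6 years with bands and 0.4 with continuous age.

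**6. Against sampling error.** At 2.05 per 10,000 and RR 1, expected events are 40,015 × 0.000205 = 8.2 and 60,714 × 0.000205 = 12.4. The SE of log RR is √(1/8.2 + 1/12.4) = 0.45. At 9.50 per 10,000 the events are 38.0 and 57.7, and the SE is 0.21. A bias of ln 1.08 = 0.077 is therefore about 0.17 to 0.37 of one SE.

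**The case against.** The strongest reply is that the protocol never says age enters as categories. II.G.5.a names which covariates enter, not their form; Table 5 is an empty reporting shell; and its layout is demonstrably not always the coding. Table 4 has "Year of new use Number n/a", while Table 5 lists one row per year. The functional form of a covariate is also ordinary material for an analysis plan, which is not at hand. This stands against any claim that the protocol has decided on banded age. It does not remove the point: year has a coding rule elsewhere and age has none, so the text as written leads to the bands.

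Three further objections also hold in part:

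- A reader might infer that age inside a band cannot be balanced at all. That is too strong. The score also includes coronary heart disease, hypertension, COPD, cardiovascular drugs, sex, year and setting, several of which may track age within a band. The calculations above use age alone and so probably overstate the residual.
- The age-related indications in Table 6 (pregnancy and menorrhagia against cancer and kidney disease) differ largely between the 19-44 band and the older ones, a contrast the bands already capture. No section shows that age predicts product choice or anaphylaxis within a band.
- A reader might infer that continuous age removes the whole problem. It does not for the quintile estimate, where 9-14% of the age confounding remains.

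**Conclusion.** The point holds as a conditional, low-severity one. As written, the propensity model is directed to a table whose only form of age is five bands, while a finer age is available at every site. If the bands are used, and if age is related within bands to both product choice and anaphylaxis, both primary estimates can keep some age confounding that a check on the bands would miss.

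Under the assumed distributions the bands leave about 15-32% of the log-scale age confounding. The null RR is then about 0.97 to 1.08; the strongest gradients tried reach 0.93 when opposed and 1.09 in the matched simulation. With weak gradients the gain from continuous age is about 1% or less.

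A reader might take this as a demonstrated bias that threatens the study's conclusion. The documents do not support that. They give no age distribution and no age gradient, and the residual is small beside the detectable RRs of 1.70-2.80, the policy threshold of 4 and the expected sampling error. The reason to act is that the improvement is systematic and costs almost nothing.

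**What to change.** In II.G.5.a and II.G.6.a, state that age on the index date enters the site propensity model and the secondary outcome regression as a continuous flexible term, for example a restricted cubic spline or linear plus quadratic. Say that the five bands in Table 5 are for description only. Report the standardised difference for mean age, as well as for the bands, before and after matching or stratification.

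The cost is a sentence in each section and a small change in the common site program. No new data are needed and patient-level age stays at the Data Partner. A quadratic uses two parameters, and a spline with up to five knots uses at most four, which is what the four band indicators would use.

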### 3. Calculation of incidence

We will calculate the incidence of anaphylaxis for new users of iron dextran and new users of other parenteral iron, with 95% CIs. We will calculate the overall incidence with and without sites with users but no anaphylaxis events and site with users of only one parenteral iron product, as well as incidence by Data Partner.

### 4. Indications of use

We will identify one or more indications for the use of parenteral iron for each patient (Table 6), using ICD-9-CM codes in the MSDD diagnosis file during 183 days prior to (and including) the index date. We will allow patients to have more than one potential indication. For those patients receiving parenteral iron who do not have any of these diagnostic codes, we will categorize as “other indication”. For patients categorized as “other indication”, we will obtain a list of all diagnostic codes within 7 days prior to the index date. Diagnostic codes for patients with “other indication” will be compiled for descriptive purposes only.

**Table 6. Potential indications for prescription of parenteral iron**

Diagnosis	Identified by ICD-9-CM code(s)
Anemia complicating pregnancy, childbirth or the puerperium	648.20-648.24
Anemia in chronic kidney disease	285.21
Intestinal malabsorption, including celiac disease	579
Chronic iron deficiency anemia secondary to blood loss (chronic); Iron deficiency anemia	280
Chronic kidney disease (stages 3-5)	585.3, 585.4, 585.5

Diagnosis	Identified by ICD-9-CM code(s)
Chemotherapy encounter	V58.11, V07.39
Chemotherapy induced anemia, cancer induced anemia	285.3, 285.22
Endometriosis	617
Esophageal cancer	150, 230.1
Esophageal varices	456.0, 456.1, 456.2
Peptic ulcer disease	531, 532, 533, 534
Intestinal cancer	152, 153, 159.0, 230.3, 230.7
Menorrhagia	626.2
Ulcerative colitis; Crohn's disease	556, 555
Uterine fibroid	654.1, 218
Stomach cancer	151, 230.2
Other	None of the above

## 5. Analysis comparing risk of anaphylaxis between parenteral iron dextran and other iron products

### a. Estimation of relative risk

We will employ two propensity score-based approaches – matching and stratification – to investigate the association between the use of iron dextran and anaphylaxis, with use of other parenteral iron products as the comparison group. We will assess the covariate balance after matching and stratification. The propensity score is defined as the probability of receiving iron dextran given the measured confounders. We use the propensity score methods as our primary approach because the number of anaphylaxis events is expected to be small and the number of confounders is relatively large. The propensity score approach overcomes this issue by allowing us to adjust for all measured confounders simultaneously through a composite summary score. We will estimate the propensity scores by site using a logistic model common to all Data Partners using the probability of receiving iron dextran as the dependent variable and covariates in Table 5 as independent variables.

Propensity score matching will be conducted within sites. We will match one iron dextran user with one other iron product user using 1:1 nearest-neighbor matching without replacement

with a caliper of 0.05. Unmatched patients will be excluded from subsequent analyses. Each Data Partner will transfer an aggregated dataset of the matched cohort, which includes only the number of users and outcome events in each treatment group, to the project team. The project team will then estimate the odds ratio of the confirmed anaphylactoid/anaphylaxis event, from the Sampson criteria, comparing iron dextran users with other iron product users. The aggregated dataset will only include the number of users and outcome events within each treatment group. By matching one iron dextran user with one other iron product user with similar propensity score, we estimate the average treatment effect among the treated (ATT). Thus, we will also do propensity score stratification to estimate the population-wide average treatment effect (ATE).

In propensity score stratification, each Data Partner will divide its entire study population (iron dextran users and other iron products users) into 5 strata based on the site-specific propensity score quintiles. Each Data Partner will transfer an aggregated dataset consisting of the within-stratum numbers users and anaphylaxis events in each treatment group. If sample size allows, the project team will fit a logistic regression model on the probability of anaphylaxis comparing the exposure groups (iron dextran vs. other iron products) stratifying both on site and within-site propensity score strata. If the number of anaphylaxis events is too small to stratify on both site and the within-site PS strata, we will consider stratifying on PS strata only or collapsing certain sites with few anaphylaxis events. The results from the propensity score matching and stratification analyses could differ if the effect of iron dextran differs among the subgroup of actual iron dextran users (ATT) versus among the entire group of all parenteral iron products users (ATE).

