## 7. Sample size calculation

From the feasibility assessment results, we estimated that there were 40,015 new iron dextran users and 60,714 new users of other iron products who did not have a diagnostic code for dialysis in the previous 183 days. We varied the baseline risks of analysis and epinephrine administration according to the modular program results, and computed the least detectable relative risk at a 0.05 significance level with a power of approximately 80% using the Fischer Exact Test. In our power calculation, we used the relative risk instead of odds ratio because the outcome variable is rare. Given the incidence of this rare outcome, the results of these approaches are identical to at least 2 decimal places (Table 7).

The workgroup determined, with the input of the FDA, that a study with enough power to detect a relative risk of four was adequate to perform a protocol-based assessment. FDA opinion determined that, given the rarity of the outcome (anaphylaxis), a relative risk of four or higher would be great enough to influence policy decisions. Because our least detectable relative risks are all smaller than four, the study has sufficient sample size for the primary objective.

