**Table 7. Sample size power calculations**

Baseline risk per 10000 patients	Relative Risk	Power
2.05	2.80	81.3%
2.15	2.70	79.6%
2.25	2.70	81.5%
2.35	2.60	79.3%
2.45	2.60	81.1%
2.55	2.55	80.7%
2.65	2.50	80.2%
7.50	1.80	80.8%
8.00	1.75	78.9%
8.50	1.75	81.4%
9.00	1.70	78.9%

Baseline risk per 10000 patients	Relative Risk	Power
9.50	1.70	81.1%

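### The sparse-event fallback for the stratified analysis drops or collapses site, contradicting the protocol's own site-stratification rule and leaving between-site differences unadjusted

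*Protocol*

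**What the plan says.** Section II.G.1 removes Data Partners without a confirmed event from the inferential analysis. Its reason is that the measure is a ratio and that "all analyses will stratify on site", so such sites carry no information. In a separate sentence it judges the "bias introduced by combing sites with different prescribing and coding practices and treating them as a single site to be potentially significant".

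Section II.G.5.a describes two propensity-score approaches. Matching is 1:1 and within site, and targets the effect in the treated (ATT). Stratification targets the effect in the whole population (ATE). On the score it says "We will estimate the propensity scores by site using a logistic model common to all Data Partners", and each site's population is cut into "5 strata based on the site-specific propensity score quintiles". The planned model stratifies on both site and within-site score stratum. If there are too few events for that, "we will consider stratifying on PS strata only or collapsing certain sites with few anaphylaxis events". No event count that triggers this is given, and nothing is said about restoring the sites already excluded for having no events.

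**The concern.** The two sections cannot both be followed. Under the fallback, not every analysis is stratified by site, and collapsing sites is the practice that II.G.1 warns against.

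There are two statistical consequences.

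- **Between-site confounding.** A site-specific quintile is a rank within a site, not a score range. The third quintile at a site that rarely uses dextran and the third quintile at a site that mostly uses it hold patients with very different probabilities of receiving dextran. Site is not among the Table 5 covariates. Pooling by rank therefore leaves site differences in dextran share and in baseline risk (or event capture) unadjusted.
- **Selection on outcome.** Dropping a zero-event site is harmless while site is a stratum. Once it is not, that site's users belong in the pooled denominators, and they have been removed because of their outcomes.

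Section II.G.5.a also says that the matched and stratified results may differ because ATT and ATE differ. Under the fallback, a gap caused by site could be read as effect heterogeneity.

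**Working it through.** **The plan's own figures.** The point disputes no stated number. Table 7 is used only for event counts. With "40,015 new iron dextran users and 60,714 new users of other iron products", tested "at a 0.05 significance level with a power of approximately 80% using the Fischer Exact Test", the first row reads "2.05 2.80 81.3" (baseline per 10,000, relative risk, power in %). Exact power of Fisher's test at one-sided 0.025 gives 80.7% for that row, and all 12 rows agree within 0.7 points.

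**How sparse the data may be.** First row, relative risk 2.8: 40,015 × 0.000205 × 2.8 = 23.0 dextran events and 60,714 × 0.000205 = 12.4 others, about 35 in total. At relative risk 1 the total is 100,729 × 0.000205 = 20.6. The upper rows of Table 7 give more: from 100,729 × 0.00075 = 75.5 (relative risk 1) to about 122 (baseline 9.5, relative risk 1.7). These events would be spread over five strata at each site. II.G.1 itself expects several sites with none.

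**Confounding, by hand.** Assume two equal sites, dextran shares 60% and 20%, baseline risks 4.1 and 2.05 per 10,000, and no drug effect. Without site strata:

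- dextran risk = (0.6 × 4.1 + 0.2 × 2.05) / 0.8 = 2.87 / 0.8 = 3.59
- other-iron risk = (0.4 × 4.1 + 0.8 × 2.05) / 1.2 = 3.28 / 1.2 = 2.73
- ratio = 1.31 instead of 1.00

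**Confounding with quintiles kept.** Assume four sites of 25,000, with dextran probability in each quintile given by the site logit plus an offset from -1.2 to 1.2. The Mantel-Haenszel odds ratio is Σ(a·d/T) / Σ(b·c/T), computed from expected counts. Here a and b are dextran users with and without an event, c and d are other users with and without an event, and T is the cell total. It was summed over quintile ranks only, then over site-by-quintile cells. The two sites with higher dextran share have the higher baseline risk.

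| Assumed dextran shares | Risk difference | Rank only, true 1.0 | Rank only, true 2.8 | Site × quintile |
|---|---|---|---|---|
| equal | any | 1.00 | 2.80 | 1.00 / 2.80 |
| 10-70% | none | 1.00 | 2.80 | 1.00 / 2.80 |
| 30-50% | 1.2-fold | 1.03 | about 2.9 | 1.00 / 2.80 |
| 30-50% | 1.5-fold | 1.06 | about 3.0 | 1.00 / 2.80 |
| 10-70% | 1.5-fold | 1.18 | 3.30 | 1.00 / 2.80 |
| 10-70% | 2-fold | 1.31 | 3.68 | 1.00 / 2.80 |
| 10-70% | 3-fold | 1.50 | 4.22 | 1.00 / 2.80 |

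With the gradient reversed and shares of 10-70%, a true 2.8 becomes 2.37, 2.11 and 1.81. The last is 1.81 / 2.80 = 0.65 of the true value.

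**Zero-event exclusion alone.** Assume the same baseline risk of 2.05 per 10,000 everywhere, so that there is no between-site confounding, with two large sites at 45% dextran and ten sites of 2,500 users. At relative risk 1 a small site has no event with probability exp(-2,500 × 0.000205) = exp(-0.51) = 0.60, so about six of the ten are dropped. In 4,000 simulated data sets per scenario with a true value of 1, the rank-only geometric-mean odds ratio moved as follows:

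| Small-site dextran share | Zero-event sites kept | Dropped |
|---|---|---|
| 10% | 0.97 | 0.79 |
| 40% | 1.00 | 0.98 |
| 80% | 1.01 | 1.23 |

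With site strata the estimates were identical whether or not those sites were dropped, as II.G.1 says.

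**The case against.** The fallback is conditional: site-by-stratum analysis comes first, and the text says only that alternatives will be considered. A reader might infer that the fallback is the path the study will probably take. The protocol gives neither the number of sites nor site-level counts, and the upper rows of Table 7 imply 76 to 122 events, so that inference is not supported. The sparse condition is realistic, and no more can be said.

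A reader might also infer that the whole primary result is exposed. It is not. Matching is 1:1 within site, so each site contributes equal numbers to both groups and dropping a site removes equal numbers from both. The outcome regression at larger Data Partners (II.G.6.a) is a further within-site check.

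Nor does the protocol concede a significant bias; it says potentially significant. The bias needs dextran share and baseline risk to move together across sites. In the 10-70% example it is close to nil when the two middle sites carry the higher risk. Collapsing only some small sites does less harm than dropping site altogether: with two sites of 40,000 kept separate and four of 5,000 collapsed, a true 1.0 becomes about 1.04 at an aligned 1.5-fold difference, against 1.18 in the table.

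Triggers and estimators are often left to an analysis plan. That explains the missing threshold. It does not remove the contradiction, because either section can be followed only by overriding the other.

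**Conclusion.** The contradiction between II.G.1 and II.G.5.a stands and should be fixed. It concerns the stratified (ATE) analysis, and only if the fallback is used. In that case the analysis adjusts for neither site nor a common score, and the zero-event exclusion loses its justification.

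The size cannot be read from the documents. Under the stated assumptions it runs from no bias (equal share or equal baseline risk, with zero-event sites kept), through 1.03 to 1.06 for a true 1.0 under modest site differences, to about 1.5, or 0.65 if reversed, under strong ones. The exclusion alone can move a true 1.0 to about 0.8 or 1.2 when small sites differ sharply in dextran share, and hardly at all when they do not. These figures show the mechanism and its range; they do not estimate the bias in this study. At the strong end a true 2.8 would be reported above the relative risk of four that II.G.7 treats as relevant to policy, but the documents do not show that the sites differ that much.

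**What to change.** Delete the fallback sentence in II.G.5.a and name an estimator that tolerates sparse strata: conditional logistic regression (exact where needed) or Mantel-Haenszel, over site-by-score-stratum cells. Neither needs many events per cell. With one event in a cell of n1 dextran and n0 other users, the cell contributes through the probability n1·ψ / (n1·ψ + n0) that the event falls in the dextran group, where ψ is the common odds ratio. Cells without events contribute nothing, so the II.G.1 exclusion remains harmless.

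If strata must still be merged, merge adjacent score strata within a site, by a rule fixed without sight of events by exposure group. If site is ever dropped in a sensitivity analysis, keep zero-event sites in the denominators and say so in II.G.1.

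The cost is a few sentences. The aggregated tables that Data Partners already send (users and events by group within each stratum) suffice. The interval may be somewhat wider, which was not calculated here, and merging strata would make the covariate adjustment coarser.
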